8.1.4.2. Subcutaneous immunoglobulin (SC Ig)

Subcutaneous immunoglobulin weekly may be used in patients who meet local criteria for home-based self-administration in centres with established SC Ig programs. Dosing is usually given at 100mg/kg/week, modified to achieve an IgG steady state level of at least the lower limit of the serum reference range.

Study participants may transition from IVIg to SC Ig, or vice versa, using a conversion factor of 1:1 for total monthly IV to SC dosing. Where IVIg is used in this protocol, unless explicitly stated, it shall be taken to include SC Ig.

8.1.5. Restarting Ig

If a participant on either of the immunoglobulin cessation intervention arms (Arm A or Arm B) experiences a Grade 3 or higher infectious complication, they may recommence IgRT, as directed by their treating clinician.

In the absence of a Grade 3 or higher infectious complication, patients will stay on their assigned treatment. However, the treating clinician may reinstate IgRT if this is deemed in the participant's best interest. This will not be regarded as an event for EFS in the primary analysis, however it will be recorded on the relevant eCRF for the purposes of supplementary analyses.

In these situations, trial participation will not end and the participant will continue to follow the schedule of assessments until M12, except in the case of patients who also choose to withdraw from the study.

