4.2. Domain-specific background

4.2.1. Overview

4.2.1.1. Duration of Ig replacement – when to cease therapy?

Evidence to guide duration of IgRT and when to cease it is limited. From the most recent Cochrane review,¹ in clinical trials of Ig replacement, the duration of therapy was for a period of between 6 and 12 months, with follow-up not extending beyond 12 months. A recent single-centre, non-randomised study showed that regular Ig replacement was able to be safely stopped in a small cohort of patients with haematological malignancies who received prophylactic antibiotics and an additional emergency-held antibiotic supply to keep at home.² To date, there have been no randomised controlled trials to guide if and when to trial cessation of Ig.

Substantial variation exists in the approach to duration of IgRT and use of alternative therapies, both internationally and within Australia.^{3,4} For patients receiving Ig for this indication, Australian government Criteria state: *“Cessation of Ig therapy should be considered at least after each 12 months” of its use.*⁵ This statement is not evidence-based, and in this group of immunocompromised patients who are highly infection prone and vulnerable, and for whom infection is their highest risk of mortality, such evidence is essential in order to recommend or mandate such a clinical management directive. UK guidelines (2019) advise that it may be appropriate to consider temporary cessation of Ig in the summer,⁶ although at least in Australia from 2009 to 2013, there was no significant seasonal change in IgRT utilisation.⁷ In New Zealand (NZ), Ig approvals are reviewed every 12 months.

There is significant variation in clinical practice with regard to duration of IgRT. In a recent survey of Australian and New Zealand haematologists, 21% reported continuing Ig unless an adverse event occurred, 24% routinely stop after a fixed duration, 15% stop if the patient is in clinical remission with recovery from hypogammaglobulinaemia, 6% stop during summer, and 34% decide on a case-by-case basis.⁴

Our current treatment decisions are not evidence-based because no data exist on optimal duration of IgRT or outcomes after stopping: cessation is recommended, but standard of care regarding the

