7.2.1. Domain inclusion criteria

1. Patients must be receiving Ig (IV or subcutaneous - SC Ig) replacement for prevention of bacterial infections due to hypogammaglobulinaemia for at least 6 consecutive months.
2. Patient is eligible for trial of Ig cessation in the opinion of the treating clinician and local investigator.

3. Willing and able to comply with each of the treatment arms.

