8.1.7. Discontinuation of study assigned treatment protocol

Site investigators/clinicians may discontinue a patient from their assigned trial treatment if this is no longer in the participant's best interest. Reasons for treatment discontinuation may include:

- Grade 3 or higher adverse event
- Grade 3 or higher infectious complication

- Unrelated medical illness or clinical condition representing potential risk, such as change to therapy for underlying malignancy
- Participant's request
- Poor compliance
- Participant is no longer deemed eligible to participate

If a participant is discontinued from the assigned treatment protocol for any reason, the end-of-treatment (EOT) visit assessments should be completed 4 weeks (+/- 7 days) after the final administration of the participant's assigned treatment. Trial participation will not end and the participant will follow the schedule of assessments until M12.

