9.2. Secondary Endpoints

All secondary endpoints specified in the Core Protocol.

Domain-specific secondary endpoints are:

1. Resumption of Ig treatment over 12 months for patients in Ig cessation treatment arms.

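### Does section 8.1.5 leave the primary analysis one-sided, because it settles Ig restart in Arms A and B but is silent on stopping Ig in Arm C?

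*Protocol*

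**What the plan says.** Section 8.1.5 concerns Arms A and B only and has two routes back to Ig.

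- After a Grade 3 or higher infection, participants are told "they may recommence IgRT, as directed by their treating clinician". No EFS status is given to that restart itself.
- Otherwise the rule is "In the absence of a Grade 3 or higher infectious complication, patients will stay on their assigned treatment", with an exception: "However, the treating clinician may reinstate IgRT if this is deemed in the participant's best interest". Of this second route the section says "This will not be regarded as an event for EFS in the primary analysis", and it has the reinstatement recorded for supplementary analyses.

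Section 8.1.7 covers discontinuation of assigned treatment in any arm, so it includes stopping Ig in Arm C. It requires an end-of-treatment visit timed from the last administration, and adds: "Trial participation will not end and the participant will follow the schedule of assessments until M12". It does not mention EFS.

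Section 9.2 adopts all secondary endpoints of the Core Protocol and adds one for the domain: "Resumption of Ig treatment over 12 months for patients in Ig cessation treatment arms".

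Sections 5.1 and 9.1 leave the EFS definition and the primary endpoint to the Core Protocol. Section 12 leaves the analysis to the Master Statistical Analysis Appendix and the domain-specific statistical analysis plan (DSSAP).

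**The concern.** Side by side, sections 8.1.5, 8.1.7 and 9.2 seem to handle crossover in one direction only. Restart in the cessation arms has a stated status in the primary analysis, a recording rule and an endpoint. Stopping Ig in the control arm has none of these in this appendix.

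Stopping in Arm C is also foreseeable. Section 7.2.1 requires of every participant: "Patient is eligible for trial of Ig cessation in the opinion of the treating clinician and local investigator". Section 4.2.1.1 cites national criteria under which cessation should be considered at least every 12 months, and a clinician survey in which "21% reported continuing Ig unless an adverse event occurred, 24% routinely stop after a fixed duration". Adding the 15% who stop in remission with recovery and the 6% who stop in summer gives 24% + 15% + 6% = 45% of clinicians with some stopping rule.

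The aim is non-inferiority and the design is open-label. If Ig protects, restart in A or B and stopping in C both pull the arms together, which favours the non-inferiority claim when the target is uninterrupted treatment in both groups. Scoring the two directions differently would change the contrast itself. A reader might also see a resumption figure for A and B without a matching figure for C.

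**Working it through.** **Step 1: what the one explicit EFS statement covers.** It follows the sentences on participants without a Grade 3 or higher infection. Read strictly, it settles discretionary reinstatement only. Restart after such an infection stands in a separate paragraph with no EFS status of its own, and whether the infection counts as an event depends on the Core Protocol. The text therefore does not give one status to every restart in A and B and withhold it from C. It gives a status to one specific route.

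**Step 2: how Arm C compares with other discontinuations.** Section 8.1.7 makes no distinction by arm. It gives no EFS status to stopping Ig in Arm C, and none to stopping prophylactic antibiotics in Arm A. The line in the text runs between discretionary reinstatement and discontinuation in general, not between cessation arms and control arm.

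**Step 3: what happens if the plan is followed as written.** A participant who stops Ig in Arm C has an end-of-treatment visit and stays on the assessment schedule to month 12. Scheduling that visit requires the date of the last administration. Nothing says that stopping is an event or that follow-up is censored, and the hypotheses in section 4.3.1 concern severe or recurrent infection, not change of treatment. Later events are still observed, as they are after restart in A or B. This is a treatment-policy comparison in both directions.

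**Step 4: size, on assumptions only.** The protocol gives no event risk, margin, sample size or crossover rate, so there is no figure to reproduce. Assume a 12-month risk of 20% on Ig and 30% off, crossover at uniform times unrelated to infection, and a hazard that switches at crossover.

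- Hazards: hC = −ln(0.8) = 0.2231; hS = −ln(0.7) = 0.3567.
- Risk of a crosser in either direction: 1 − (0.8 − 0.7)/(0.3567 − 0.2231) = 25.1%.
- Cessation arm with restart fraction r: 30.0 − 4.89r points. Arm C with stopping fraction q: 20.0 + 5.11q points.
- Chance of declaring non-inferiority, with an assumed 10-point margin and one-sided 2.5%: Φ(−1.96 + (10 − diff)/SE), where SE² is the sum of the two binomial variances, each divided by n per arm.
- Example, r = q = 20%: 30.0 − 0.98 = 29.02 and 20.0 + 1.02 = 21.02, a difference of 8.0 points. With n = 100, SE = 6.10 points and the chance is Φ(−1.96 + 0.33) = 5.1%. With n = 300, SE = 3.52 points and it is Φ(−1.96 + 0.57) = 8.2%.

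| Crossover in both directions | Difference (points) | Chance of declaring non-inferiority, n = 100 to 300 per arm |
|---|---|---|
| 10% | 9.0 | 3.6% to 4.7% |
| 20% | 8.0 | 5.1% to 8.2% |
| 40% | 6.0 | 9.6% to 20.4% |

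Stopping in Arm C alone at 10%, 20% and 40% gives 9.5, 9.0 and 8.0 points. If Ig does not protect, every shift is zero.

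**Step 5: what these figures mean.** They exceed 2.5% only against a target of uninterrupted cessation versus uninterrupted Ig. For the strategies of stopping with restart if needed against continuing with stopping if needed, the smaller difference is the true difference, and there is no excess error. The restart part may also be overstated. If the Grade 3 or higher infection that opens the first route is itself an EFS event under the Core Protocol, which cannot be seen here, a later restart cannot change the time to first event.

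**Step 6: the asymmetric scenario.** If stopping in Arm C were scored as an event, 10% stopping would raise Arm C failure from 20% to 20% + 10% × 80% = 28%. That would matter, but no sentence in the protocol prescribes or suggests it.

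**The case for a change.** The strongest opposing case is that this appendix did not simply defer. It chose to fix the primary-analysis status of one kind of crossover, and it owns the list of domain endpoints. Stopping Ig in the control arm is specific to this domain, so its natural place would be beside the restart rule. In an open-label non-inferiority trial, fixing both directions in advance prevents a choice made after the data are seen, and the cost would be a sentence.

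Part of this stands. The asymmetry is in the text, both crossovers do narrow the contrast if Ig protects, and a cross-reference, with a clearer statement of which restarts section 8.1.5 means, would help the reader. That is an editorial convenience.

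The rest does not stand. Intercurrent-event handling and supplementary analyses commonly sit in the statistical analysis plan, and section 12 sends them there. The reference list includes the ICH addendum on estimands and a paper on estimands in haematologic oncology, which the visible text does not cite; this suggests, without proving, that a companion module deals with the matter. That Arm C will lack a matching figure cannot be asserted while the Core secondary endpoints are unseen. The survey reports shares of clinicians in routine practice, not a stopping rate among participants assigned to continue, whom sections 8.1.4 and 8.1.6 keep on Ig for 12 months.

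**Conclusion.** The concern does not hold. The restart rule is coherent as treatment policy, section 8.1.7 keeps discontinued participants of every arm under observation to month 12, and nothing scores stopping Ig in Arm C as an event. What remains is that this appendix does not spell out a status or an endpoint for Arm C stopping. It hands the EFS definition, the Core endpoints and the analysis to documents that are not at hand, so the silence cannot be called a gap in the plan. A further supplementary analysis of crossover would be a preference, not the correction of an error.

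No size can be drawn from the protocol. The illustrative narrowing, from 10.0 points to between 9.0 and 6.0, rests wholly on assumed risks, margin, sample size and crossover rates, and describes dilution against a target of uninterrupted treatment. The conclusion rests on the text as it stands. It would change if a companion document scored stopping Ig in Arm C as an event while leaving restart unscored, or censored one direction and not the other.

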8.1.6. Duration of therapy

Participants will remain on assigned treatment for 12 months. Participants do not need to stop their trial-assigned treatment at 12 months, but all treatment decisions including for prevention of infection after completion of trial treatment (at 12 months from Day 1 of study) will be managed by the participant's treating clinician.

8.1.7. Discontinuation of study assigned treatment protocol

Site investigators/clinicians may discontinue a patient from their assigned trial treatment if this is no longer in the participant's best interest. Reasons for treatment discontinuation may include:

- Grade 3 or higher adverse event
- Grade 3 or higher infectious complication

- Unrelated medical illness or clinical condition representing potential risk, such as change to therapy for underlying malignancy
- Participant's request
- Poor compliance
- Participant is no longer deemed eligible to participate

If a participant is discontinued from the assigned treatment protocol for any reason, the end-of-treatment (EOT) visit assessments should be completed 4 weeks (+/- 7 days) after the final administration of the participant's assigned treatment. Trial participation will not end and the participant will follow the schedule of assessments until M12.

8.1.8. Concomitant care

All other aspects of care, including other antimicrobial prophylaxis (including antivirals, antifungals) and vaccinations, will be according to usual care and local practice. For example, patients already taking low-dose (80mg/400mg) daily or intermittent (three times a week) co-trimoxazole for *Pneumocystis jirovecii* pneumonia (PJP) prophylaxis may continue, if necessary with a dose increase if allocated to Arm A. Higher doses of PJP prophylaxis are not permitted in the immunoglobulin treatment arm.

It is recommended that all participants receive routine vaccinations, including pneumococcal, influenza and COVID-19 vaccines, as part of their usual care, and have measurement of pre- and post-vaccination pneumococcal responses, where polysaccharide pneumococcal vaccine is due to be given on study.

Patients who are commenced on therapy to treat underlying malignancy may continue on the study. Patients may receive granulocyte colony stimulating factor (G-CSF) for prophylaxis or treatment of neutropenia according to local guidelines.

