7.2.2. Domain exclusion criteria

1. Prior or planned allogeneic haematopoietic stem cell transplantation.
2. Major infection (Grade 3 or higher) in preceding 3 months, and/or current active infection requiring systemic antimicrobial treatment.
3. Already receiving systemic antibiotic prophylaxis for the purpose of preventing bacterial infection (NB: patients may receive antiviral, antifungal and PJP prophylaxis).
4. Intolerance of all trial antibiotic options in either arm A or arm B.
5. Communication, compliance or logistical issues (e.g. living long distance from medical facility) that are likely to limit a patient's ability to take prophylactic or emergency antibiotics, or to obtain urgent medical attention for symptoms of infection.
6. Pregnant or breastfeeding.
7. Severe renal impairment (estimated or measured creatinine clearance of <30mL/min).
8. Previous splenectomy.
9. Previous participation in this domain
10. Treating team deems enrolment in the domain is not in the best interests of the patient.

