8. TREATMENT OF PARTICIPANTS

8.1. Interventions

8.1.1. Interventions

This domain has three interventions:

- Immunoglobulin cessation and commencement of prophylactic antibiotics (Arm A)
- Immunoglobulin cessation without prophylactic antibiotics, with a supply of oral antibiotics immediately available (at home) for emergency use (Arm B)
- Continuation of immunoglobulin replacement at current dose and schedule (Arm C)

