8.1.2. Immunoglobulin cessation and commencement of prophylactic antibiotics (Arm A)

Participants will be treated with once daily trimethoprim-sulfamethoxazole (co-trimoxazole) 160mg/800mg, with dose adjustments as listed below, from study day 1. For patients with hypersensitivity to co-trimoxazole, or who are taking a medication with potential for a significant interaction with co-trimoxazole as outlined below, 100mg doxycycline daily will be permitted as an alternative prophylactic antibiotic. If participants encounter cytopenias which are exacerbated by the study antibiotics, participants can be switched to the other antibiotic. Participants must be able to tolerate at least one of the study antibiotics to be eligible for entry into the study.

Medications which cannot be administered with co-trimoxazole include (but are not limited to): antiarrhythmics (dofetilide, amiodarone), antivirals (amantadine/memantine, lamivudine), antineoplastics (paclitaxel), antibiotics (dapsone). Co-trimoxazole may increase the effect of the following agents, and increased monitoring of their drug levels and/or effect is required if co-administered with co-trimoxazole: digoxin, phenytoin, warfarin, oral hypoglycaemics (repaglinide, rosiglitazone, pioglitazone, glipizide), methotrexate, drugs that cause potassium retention (such as ACE inhibitors) and cyclosporin (increased monitoring of renal function).

Medications which cannot be administered with doxycycline include (but are not limited to): isotretinoin, etretinate and methoxyflurane. Doxycycline may increase the effect of the following agents, and increased monitoring of drug levels and/or effect is required if co-administered with doxycycline: warfarin, cyclosporin, phenytoin.

8.1.2.1. *Co-trimoxazole dose adjustments for cytopenias and renal impairment*

For participants with grade 2 or greater anaemia, neutropenia or thrombocytopenia, whether attributed to concomitant medications, underlying haematologic disorder or co-trimoxazole itself, the dose of co-trimoxazole may be reduced by 50% (to 80/400mg daily) at the discretion of the investigator.

Co-trimoxazole dose will be adjusted for participants with renal impairment, defined by eGFR (or, if available, measured creatinine clearance)

eGFR or creatinine clearance	Dose
> 50 mL/Min	Full dose (160/800mg)
30 to 50 mL/Min	50% dose reduction (to 80/400mg)
< 30 mL/Min	Consider switching to doxycycline, or discontinue study treatment

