8.1.3. Immunoglobulin cessation without commencement of prophylactic antibiotics (Arm B)

Patients will be provided with amoxycillin/clavulanic acid 1750-2000mg/250mg and ciprofloxacin 750mg to keep at home for initial use if symptoms of infection develop, with immediate review by their treating clinical team, or nearest emergency department or medical practitioner with phone contact to treating team if most practical and as clinically required. Diagnosis and management of the infection will be determined by the severity of the suspected infection and coordinated by the patient's treating team.

For patients with hypersensitivity to penicillin, or taking a medication with a significant interaction with amoxycillin/clavulanic acid, clindamycin 600mg is permitted as an alternative to amoxycillin/clavulanic acid. If the patient has a contraindication to ciprofloxacin, this antibiotic will be omitted from the emergency antibiotics. Contraindications to ciprofloxacin include quinolone hypersensitivity (including nalidixic acid) and concurrent tizanidine.

For participants assigned to Arm B, Day 1 of treatment is considered the date of randomisation.

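### Section 8.1.8 caps the PJP co-trimoxazole dose in the comparator (Arm C) but states no cap for Arm B, the arm meant to be free of prophylactic antibiotics

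*Protocol*

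**What the plan says.** Section 8.1.8 (Concomitant care) starts from a general rule. Other aspects of care, "including other antimicrobial prophylaxis (including antivirals, antifungals) and vaccinations, will be according to usual care and local practice". It then gives an example: patients already on co-trimoxazole for PJP, either 80/400 mg daily or three times a week, "may continue, if necessary with a dose increase if allocated to Arm A". It closes with the single restriction: "Higher doses of PJP prophylaxis are not permitted in the immunoglobulin treatment arm".

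Four other places bear on how this applies to Arm B:

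- Section 7.2.2, criterion 3, excludes patients "Already receiving systemic antibiotic prophylaxis for the purpose of preventing bacterial infection (NB: patients may receive antiviral, antifungal and PJP prophylaxis"). PJP prophylaxis is thus exempted, and no dose ceiling is attached.
- Section 8.1.1 defines the arm as "Immunoglobulin cessation without prophylactic antibiotics, with a supply of oral antibiotics immediately available (at home) for emergency use (Arm B").
- The heading of section 8.1.3 speaks of not commencing prophylactic antibiotics. The text beneath it deals with the emergency supply and does not mention PJP prophylaxis.
- Section 8.1.5 says: "In the absence of a Grade 3 or higher infectious complication, patients will stay on their assigned treatment".

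The drug concerned is also Arm A's trial treatment. Section 8.1.2 states: "Participants will be treated with once daily trimethoprim-sulfamethoxazole (co-trimoxazole) 160mg/800mg", subject to dose adjustments.

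**The concern.** Co-trimoxazole is both the usual-care PJP drug in section 8.1.8 and the active prophylaxis under test in Arm A. A ceiling on its background use is therefore part of keeping the arms distinct. The protocol writes that ceiling for the comparator and not for the experimental arm that is supposed to have no antibiotic prophylaxis.

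The second hypothesis in section 4.3.1 is that Arm B is non-inferior to continued immunoglobulin. If some Arm B participants receive near-Arm A doses and Arm C participants may not, any protective effect of the extra dose is credited to Arm B. In a non-inferiority comparison that error favours the claim. The same exposure would make Arms A and B more alike, which bears on the question in section 4.3 of whether antibiotics are needed once immunoglobulin stops. Treatment is open-label (section 10.3), so clinicians know which participants have stopped immunoglobulin without prophylactic cover. Arm A versus Arm C, the first hypothesis, is not affected.

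**Working it through.** The protocol has no figure to reproduce here. The check is a reading of the rules by arm, followed by a dose contrast. I take a higher dose to mean anything above the two PJP regimens named in section 8.1.8.

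**Which arm is barred.** Section 8.1.5 groups Arms A and B as the immunoglobulin cessation arms, and section 8.1.1 makes Arm C the only arm that continues immunoglobulin. The restriction names one arm, so it is Arm C.

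**What each arm's rule is.**

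| Situation | Arm B | Arm C |
|---|---|---|
| Already on a low PJP dose | May continue | May continue |
| Low dose raised on study | Implied not: an increase is mentioned only for Arm A | Barred expressly |
| Enters on a higher PJP dose | No rule stated | Barred expressly |
| Starts a higher PJP dose on study | No rule stated; local practice applies | Barred expressly |

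**Whether the Arm B definition fills the two empty cells.** It does so only in part.

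1. Criterion 3 of section 7.2.2 separates PJP prophylaxis from prophylaxis against bacterial infection, and section 8.1.8 lets low-dose PJP co-trimoxazole continue without restriction by arm. An arm without prophylactic antibiotics therefore cannot mean an arm without PJP co-trimoxazole, and the definition gives no dose at which one becomes the other.
2. A participant who enters on a higher dose does not commence anything, so the heading "Immunoglobulin cessation without commencement of prophylactic antibiotics (Arm B") does not reach that case.
3. Staying on assigned treatment (section 8.1.5) does not settle the PJP dose, because that dose is concomitant care and section 8.1.8 leaves it to local practice.
4. The definition of Arm C does not include prophylactic antibiotics either, yet the authors wrote an express bar for it. The same reason applies to Arm B.

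**Dose contrast.** Weekly co-trimoxazole, as trimethoprim/sulfamethoxazole:

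- Arm A full dose: 7 × 160/800 = 1120/5600 mg.
- Low-dose daily PJP: 7 × 80/400 = 560/2800 mg. Ratio 1120/560 = 2.0.
- Three times a week at an assumed 160/800 mg: 3 × 160/800 = 480/2400 mg. Ratio 1120/480 = 2.33.
- Three times a week at an assumed 80/400 mg: 3 × 80/400 = 240/1200 mg. Ratio 1120/240 = 4.67.

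The tablet strength for the intermittent regimen is not stated, so the last two lines give a range. These are dose ratios and do not estimate bias. Turning them into an effect on event-free survival would need the share of Arm B participants on a higher dose and the benefit of higher over low dose. The document gives neither.

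**The case against.** The strongest reply is that Arm B is already constrained and that few participants could fall into the gap. Daily 160/800 mg is Arm A's assigned treatment, so giving it in Arm B would go against the plain sense of that arm. The third inclusion criterion in section 7.2.1 also requires every patient to be prepared and able to follow any of the three arms, and section 7.3 allows no exceptions to eligibility. A patient who needs a higher PJP dose cannot comply with Arm C and is ineligible. Starting 160/800 mg daily for PJP on study is hypothetical, because the protocol itself describes PJP prophylaxis as low-dose or intermittent. Section 8.1.2.1 accepts 80/400 mg daily as a reduced Arm A dose, so much of the overlap between arms is already tolerated by design. Finally, extending the bar would lower PJP cover in people who have just lost immunoglobulin, and section 8.1.7 is an awkward escape because its end-of-treatment visit is timed from a last administration that Arm B does not clearly have.

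Much of this stands as a limit on size. The inclusion criterion removes patients who cannot step down, and the benefit of the extra dose may be modest. Patients who take a higher dose but could step down remain eligible, and they would be told to do so in Arm C and not in Arm B. Those same patients have already accepted Arm C's limit in order to enter, so applying it in Arm B asks nothing new of them. The difficulty with timing the end-of-treatment visit in Arm B is fair, but it would concern only the rare participant for whom stepping down proves unsuitable.

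**Conclusion.** The concern holds as a minor point. This appendix expressly caps PJP co-trimoxazole in Arm C and states no cap in Arm B for participants who enter on, or start, a higher dose. The dose that could be reached is 2.0 times the low daily PJP regimen. Any bias would run toward non-inferiority in Arm B versus Arm C and toward no difference in Arm A versus Arm B. Its size cannot be derived and may be small. Low-dose PJP use, which is permitted in both Arm B and Arm C, is not at issue.

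The conclusion rests on two assumptions: that a higher dose means one above the regimens named in section 8.1.8, and that the Core Protocol, which was not available, does not already set a limit for Arm B.

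**What to change.** In the last sentence of that paragraph of section 8.1.8, replace the reference to the immunoglobulin arm with *Arm B or Arm C*. The hypotheses need no rewording.

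The change adds no patients, visits or data. Section 2 requires a separate ethics application for each change to a domain appendix, so it is best carried with the next amendment. An Arm B participant on a higher PJP dose would have to move to the low-dose or intermittent regimen, as Arm C already requires. Where that is not in the participant's interest, section 8.1.7 allows assigned treatment to be discontinued with follow-up continuing to month 12.
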